#### 7.4.3 Derived Data for the Exploratory Endpoints

N/A

#### 7.4.4 Derived Data for the Safety Endpoints

Time to Event will be defined as: Start Date – Operative Date

Duration = End Date - Start Date

Start Date for AE will be based on Original AE Report Date. For AEs where resolution has occurred:

End Date for AE will be based on the AE Stop Date or Death Date.

When there is a Follow-up AE, the end date will come from the AE Stop Date or Death Date on the latest or highest numbered Follow-up AE.

For the Serious AE listing,

Duration = End Date - Start Date

Start Date for SAE will be based on SAE Report Date. For SAEs where resolution has occurred:

#### **CONFIDENTIAL AND PROPRIETARY**

This document contains information that is confidential and proprietary to Smith & Nephew PLC and Smith & Nephew, Inc. and is intended for use only by Smith & Nephew and its manufacturer. It shall not be reproduced or copied in whole or in part, nor shall the contents be disclosed by any means without prior written permission from Smith & Nephew, nor shall anyone make any use of it that is contrary to the expressed or implied wishes of Smith & Nephew.

Statistical Analysis Plan	
Safety and Performance of Q-Fix ® All-Suture Anchor System	Number: 17-5010-11
	Version: 2.0, 23-Oct-2019
	Page: 14 of 20

End Date for SAE will be based on the AE Stop Date or Death Date as found in the Related AE.

When there is a Follow-up AE, the end date will come from the AE Stop Date or Death Date on the latest or highest numbered Follow-up AE.

Also, a check will be performed for all bilateral knee subjects to remove from the AE summaries the double entries referencing the same Adverse Event for a single implant twice. Where an AE CRF is filled out regarding the contralateral knee after an AE has already been reported for the ipsilateral knee.

An ADE is defined as an Adverse Event that is Possibly or Probably Related to Device or Procedure.

The Expectation variable on the AE CRF is only to be filled out for Serious ADEs.

All Adverse Events will be assessed by the Investigator to determine relatedness and severity. The AEMB may subsequently classify events into SAEs, ADEs, SADEs, UADEs, USADEs etc. All safety Tables will presented based on the Investigator's and/or AEMB classifications.

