14.1.2 Adverse Device Effect

An ADE is an adverse event that, in the opinion of the Investigator, is related to the IP or the procedure.

Not Related - An AE is considered to be not related to the use of an IP or the procedure when the effect is DEFINITELY UNRELATED or UNLIKELY to have any relationship to the use of the IP or the procedure;

CONFIDENTIAL AND PROPRIETARY

This document contains information that is confidential and proprietary to Smith & Nephew PLC and Smith & Nephew, Inc. and is intended for use only by Smith & Nephew and its manufacturer. It shall not be reproduced or copied in whole or in part, nor shall the contents be disclosed by any means without prior written permission from Smith & Nephew, nor shall anyone make any use of it that is contrary to the expressed or implied wishes of Smith & Nephew.

Study Protocol—Device	
Safety and Performance of Q-Fix™ All-Suture Anchor System	Number: 17-5010-11
	Version: 2.0 05SEP2019
	Page: Page 33 of 62

Related – An AE is considered to be related to the use of an IP or the procedure when there is a POSSIBLE, PROBABLE, or DEFINITE relationship between the AE and the use of the IP or the procedure.

An ADE is further categorized depending on whether the criteria in section 14.1.3 and 14.1.4 are met.

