14.2 REPORTING PROCEDURES

AEs of any kind and DevDs will be recorded in the applicable CRF and source notes. The Investigator will evaluate all AEs for relationship to the device and procedure, if applicable, seriousness, and severity.

CONFIDENTIAL AND PROPRIETARY

This document contains information that is confidential and proprietary to Smith & Nephew PLC and Smith & Nephew, Inc. and is intended for use only by Smith & Nephew and its manufacturer. It shall not be reproduced or copied in whole or in part, nor shall the contents be disclosed by any means without prior written permission from Smith & Nephew, nor shall anyone make any use of it that is contrary to the expressed or implied wishes of Smith & Nephew.

Study Protocol—Device	
Safety and Performance of Q-Fix™ All-Suture Anchor System	Number: 17-5010-11
	Version: 2.0 05SEP2019
	Page: Page 35 of 62

ADEs, SAEs, and DevDs will be submitted/entered into the CRF and reported to the Sponsor within 24 hours of the Investigator being informed about the event (Figure 14.2-1). For ADEs and DevDs, details of the product/procedure related to the event will be included and where applicable, pictures taken of the device. The deficient product should be retained for return to the sponsor unless it is contaminated (e.g. used dressings must not be retained). Updates to submitted information will be recorded in the CRF within 24 hours of the information being available to the Investigator.

[figure not shown]
All SAEs and ADEs will be reviewed by a medically qualified person appointed by the Sponsor to determine which, if any, meet criteria for expedited reporting to the regulatory authorities. The Investigator will inform the IRB of AEs according to the IRB requirements.

Depending on the nature of the AE, the Sponsor may request copies of the subject’s medical records, imaging, operative notes, as well as results of any relevant laboratory tests performed or other documentation related to the AE. If the subject was hospitalized, a copy of the discharge summary may be requested by the Sponsor and should be forwarded as soon as it becomes available. In certain cases, the Sponsor also may request a letter from the Investigator that summarizes the events related to the case.

CONFIDENTIAL AND PROPRIETARY

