#### 7.9.4 Safety Analysis

The total number of AEs, and the total number of subjects experiencing an AE will be presented by Classification from the Investigator and the AEMB as per the tables below. 

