**7.11 Changes in Analysis Methods Specified in the Protocol**

N/A

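### SAP 7.4.4 leaves definite relatedness out of the ADE rule and starts AE/SAE Duration at the report date: wrong as written, with a minor, conditional effect

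*SAP*

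**What the plan says.** **ADE rule.** SAP 7.4.4 gives this definition: "An ADE is defined as an Adverse Event that is Possibly or Probably Related to Device or Procedure". Protocol 14.1.2 calls an event an ADE if it, "in the opinion of the Investigator, is related to the IP or the procedure", and it treats an event as related "when there is a POSSIBLE, PROBABLE, or DEFINITE relationship between the AE and the use of the IP or the procedure". SAP 7.11, headed "Changes in Analysis Methods Specified in the Protocol", is marked not applicable.

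**Who classifies.** Under SAP 7.4.4 the Investigator assesses relatedness and severity. It then adds: "The AEMB may subsequently classify events into SAEs, ADEs, SADEs, UADEs, USADEs etc". The safety tables are to rest on the Investigator's "and/or AEMB classifications". SAP 7.9.4 says that the number of AEs and "the total number of subjects experiencing an AE will be presented by Classification from the Investigator and the AEMB". The protocol text supplied does not name an AEMB. Its section 14.2 has SAEs and ADEs reviewed by "a medically qualified person appointed by the Sponsor", who decides which need expedited reporting.

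**Duration.** SAP 7.4.4 sets Duration as End Date minus Start Date. Start Date is the report date on the original AE report, or the SAE report date for SAEs. End Date is the stop date or date of death. Time to Event uses the same Start Date. SAP 7.9.4 puts Duration in the AE listing, and SAP 7.4.4 gives the formula again for the SAE listing.

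**The concern.** Device-related AEs and SAEs are a named safety endpoint (SAP 5.3). An ADE rule that stops at probable leaves out the events with the strongest causal judgement, and no reason is given. The SAP says that it is built on protocol version 2.0 and declares no departure, so this is an undeclared conflict between the two documents.

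The Duration rule measures from when an event was reported, not from when it began. In a prospective study the gap is often short. Here, sites collect the AEs accumulated since surgery at chart review (protocol 11.1.2), in subjects who must be more than 6 months post-operative (protocol 9.3). Protocol 14.2 ties reporting to when the Investigator is informed, which need not be close to onset.

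**Working it through.** The documents attach no figure to either rule, so there is none to reproduce. The check compares the texts and then works the arithmetic.

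**1. Relatedness levels counted as an ADE**

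| Level | Protocol 14.1.2 | SAP 7.4.4 |
|---|---|---|
| Possible | yes | yes |
| Probable | yes | yes |
| Definite | yes | not named |

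The protocol counts three levels and the SAP counts two.

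**2. Where a definite event would go.** The SAP 7.9.4 tables have two relationship columns. Under the literal SAP sentence, a definite event that is not an ADE can only fall in the non-device-related column:
- a non-serious event moves from ADE to AE;
- a serious event moves from ASADE or USADE to SAE.

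The event is thus re-filed as unrelated, and the total number of AEs stays the same.

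**3. Size for the ADE rule.** If k of R related events are rated definite, the literal rule counts R − k and the protocol rule counts R. With R = 10 (assumed) and k = 0, 1, 2 or 5, the literal rule gives 10, 9, 8 or 5.

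At subject level, the table shells show a percentage without a denominator. I assume all enrolled subjects.
- Enrolled at amendment 1 (protocol 23.3): 106 + 99 + 24 = 229. One subject is 1/229 = 0.44 percentage points.
- Maximum enrolment (SAP 6.1): 450. One subject is 1/450 = 0.22 percentage points.

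This applies only to a subject whose sole related event is definite.

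**4. Duration**
- SAP Duration = stop − report.
- True Duration = stop − onset.
- Error = SAP − true = onset − report.

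Protocol 9.3 excludes subjects at or below 6 months. Taking 6 months as the 182 days of the visit schedule, an event first reported at chart review is reported on day 183 or later. All onset and stop days below are assumed, as is report day 400. They show the mechanism and are not estimates.

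| Case | Onset | Stop | Report | True Duration | SAP Duration | Error |
|---|---|---|---|---|---|---|
| A | 10 | 200 | 183 | 190 | 17 | −173 |
| B | 14 | 35 | 183 | 21 | −148 | −169 |
| C | 10 | 40 | 400 | 30 | −360 | −390 |

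Duration is negative when the event resolved before it was reported (B and C). It is too short when the event was reported after onset but before resolution (A). Time to Event becomes 183 instead of 10 in case A, but the SAP names no output for it. If the CRF field holds onset, every error is zero.

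**5. What is not touched.** SAP 7.4.1 and 7.4.2 derive the 6- and 12-month re-intervention counts from revision and surgery dates. Neither rule enters those counts.

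**The case against.** The strongest reply is that the planned tables do not run on the SAP sentence. They follow Investigator and/or AEMB classifications, and under protocol 14.1.2 ADE status is the Investigator's opinion with definite included. That stands: Investigator-based tables that follow the protocol lose nothing.

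A reader might infer that the SAP will drop definite events, or that the AEMB applies the narrower definition. The documents support neither. They do not say which definition the AEMB uses. What remains is that the only definition placed beside the AEMB's role is the narrow one, and that a programmer could derive the cells from it.

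Other protection also counts. The AE listing carries the Investigator's relationship assessments. Protocol 12.4 promises AE summaries by relationship to the device, although SAP 7.9.4 shows no table for them.

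The SAP sentence ends in a reference mark 1. SAP reference 1 is a study of intraoperative anchor pullout, which does not evidently bear on an ADE definition. A footnote lost in text extraction cannot be ruled out.

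On Duration, a reader might infer that the listings will certainly hold negative values. The CRF is not available, and the report-date field may hold onset. Protocol 14 also foresees events already reported to the sponsor, for which the gap may be smaller. So the fault is in the stated rule, and its effect depends on the field.

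Two further points might be read as errors. The and/or wording fits an AEMB that may, but need not, classify. The SAP's device-related column also holds procedure-only events. However, protocol Table 14.1-1 itself heads its first column as not device-related, and relabelling would still give no device-only count. Neither point requires a change.

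**Conclusion.** Wrong as written, with minor effect. The ADE definition conflicts with protocol 14.1.2 without a declared change; confidence in that is high. Its effect ranges from zero, where classifications follow the protocol, to 0.22–0.44 percentage points for each affected subject if the SAP sentence is used literally. That range assumes a denominator of all enrolled subjects, and the number affected is unknown.

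The Duration rule is unsound for a retrospective chart review unless the report-date field holds onset; confidence there is moderate. It reaches only the AE and SAE listings. The primary and 12-month endpoints, their intervals and total AE counts do not change.

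**What to change.** In SAP 7.4.4:

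1. Define an ADE as possibly, probably or definitely related, by reference to protocol 14.1.2, and state that this holds for both the Investigator and the AEMB classification.
2. Check the CRF date field and base Start Date on the recorded onset date. Leave Duration blank when onset is missing or partial, in line with the no-imputation policy of SAP 7.3.
   - If the report-date field already holds onset, only rename it in the SAP.
   - If the CRF has no onset field, omit Duration and list the recorded report and stop dates.

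Settling the and/or wording and relabelling the table columns are optional.

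The cost is SAP wording, minor programming and one look at the CRF. Some durations will be blank, and ADE counts may be slightly higher than under the literal rule.

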## 7.5 Baseline Data

### 7.5.1 Demographics and Baseline Characteristics

Patient demographics including age, gender, and body mass index (BMI) will be summarized using appropriate descriptive summary characteristics.

### 7.5.2 Medical History

Primary Diagnosis, previous surgeries, Joint Involvement, and pre-operative mechanical alignment will be summarized using appropriate descriptive summary characteristics.

### 7.5.3 Operative

Intervention, Skin to skin summarized using appropriate descriptive summary characteristics.

### 7.5.4 Discharge Information

Prophylactic Antibiotics given, DVT Prophylaxis given, and other pertinent discharge information will be summarized using appropriate descriptive summary characteristics.

## 7.6 Disposition of Subjects

Patient accounting will be presented as follows:

- Complete Data Per Protocol: Subjects with complete data for the primary endpoint, evaluated per protocol, in the window time frame.
- Any Data: Subjects with any follow-up data reviewed or evaluated by investigator (“all evaluated” accounting).
- Theoretically Due: Number of subjects that would have reached the beginning of the study window associated with each visit if all subjects returned.
- Not Yet Overdue: Subjects who have not yet returned visited but whose visiting window is still open.
- Deaths: Cumulative number of subjects that died during or prior to the study visit.
- Revision: Cumulative number of subjects that failed (revision) during or prior to the study visit.
- Expected Visit: Theoretical subjects minus the number of deaths and revisions.
- % Follow-up: Any Data/Expected\*100
- % Follow-up Per Protocol: Complete Data Per Protocol / Expected \*100

Additionally information on subjects discontinued from the study prematurely will be presented, with a breakdown of the reasons for discontinuation as reported in the CRF. The disposition table will be based on the population from the Safety Population. A Disposition table will also be created in order to summarize the outcomes in terms of implants.

## 7.7 Protocol Deviations

A protocol deviation is defined as an instance of failure, intentionally or unintentionally, to follow the requirements of the protocol. Protocol deviations include, but are not limited to: study visits outside the window or missed, failure to capture patient reported outcomes at defined time points, failure to conduct radiologic or clinical evaluation at defined time points, failure to collect adverse events at defined time points, and failure to withdraw subjects defined by protocol withdrawal measures. Specificity and determination of deviations that would warrant exclusion of subjects from the PP population will be finalized prior to database lock.

A listing of all protocol deviations encountered on-study will be provided.

## 7.8 Multiplicity

N/A

## 7.9 Evaluation of Efficacy

### 7.9.1 Analysis of Primary Endpoint

- Overall clinical success rate at 6 months will be summarized using count (n) and percentage (%). A 95% Confidence Interval (CI) for the percentage of subjects with clinical success at 6 months will be computed using exact methods. This same analysis will be repeated by the position, i.e. the hip, shoulder and knee will be reported. These analyses will be carried out using the per protocol population as the primary analysis population with the safety population used for sensitivity analyses.

### 7.9.2 Analysis of Secondary Endpoints

- Clinical success rate at 12 months will be analyzed using the same type of analysis carried out on the primary endpoint.
- Clinical success rate at 6 months and at 12 months for subjects 13 to 21 years of age will be analyzed using the same type of analysis carried out on the primary endpoint.
- Device-related re-intervention. All the above variables will be categorical in nature hence frequencies together with percentages will be tabulated for the entire sample as well as by the indication. Available data will be summarized and summary statistics tabulated. For both the ROM and VAS secondary endpoints a 95% Confidence Interval (CI) for the percentage of subjects with clinical success at 6 months and 1 year will be computed using exact methods

### 7.9.3 Exploratory Analysis

- Clinical success rate at 6 months and at 12 months for all subjects will be analyzed by anchor size.

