5. INTRODUCTION

5.1 BACKGROUND

Bone anchor fixation devices are typically indicated for a variety of repairs in the shoulder, elbow, hand/wrist, hip, knee and foot/ankle. There are numerous alternative therapy options associated with these indications including conservative therapies such as rest, nonsteroidal anti-inflammatory drugs (NSAIDs), injection of steroids with lidocaine, and physical therapy. Several clinical studies were identified that reported higher clinical outcomes, or the ability to return to previous level of activity^{1,2}, or lower complication/reinjury rate^{2,3} in patients that were treated surgically rather than conservatively. When conservative therapy does not offer relief of symptoms for the patient, surgical intervention is often recommended. One method of surgical intervention is to repair using an implant such as an interference screw or suture anchor. Interference screws provide a press fit between bone to bone, or bone to graft/tendon whereas suture anchors approximate soft tissue with an implant embedded in the bone. The use of suture anchors may provide advantages such as reduced operative time, ease of access to the site of implantation, improved suture material, decreased stress along the suture line, greater repair strength, and improved consistency of load-to-failure characteristics⁴⁻⁷. Patient bone density, repair location, potential allergies, the operation being performed and surgeon preference determine the size, type and composition of the anchor needed to secure the soft tissue to the bone⁸.

Non-absorbable, soft suture anchors have recently been introduced for use in arthroscopic or open soft tissue to bone reattachment. Soft suture anchors or all-suture anchors are completely suture-based implants. The anchors usually come with single or double loaded suture options. Soft anchors are usually smaller than hard anchors; hence the volume of bone removed is less, which is especially helpful should subsequent revision be necessary⁹⁻¹⁰. Additionally, the small size enables placement of anchors in very close proximity to each other allowing multiple sutures/fixation points per unit area of soft tissue⁹. The few studies that have investigated all-suture anchor biomechanics, such as cyclic loading and pullout mechanics, suggest that they are comparable to traditional anchors¹⁰⁻¹³. Soft anchors have also been

CONFIDENTIAL AND PROPRIETARY

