This document contains information that is confidential and proprietary to Smith & Nephew PLC and Smith & Nephew, Inc. and is intended for use only by Smith & Nephew and its manufacturer. It shall not be reproduced or copied in whole or in part, nor shall the contents be disclosed by any means without prior written permission from Smith & Nephew, nor shall anyone make any use of it that is contrary to the expressed or implied wishes of Smith & Nephew.

Study Protocol—Device	
Safety and Performance of Q-Fix™ All-Suture Anchor System	Number: 17-5010-11
	Version: 2.0 05SEP2019
	Page: Page 14 of 62

reported to provide a comparable, or even higher, mechanical strength than that measured for the interference screw technique¹⁴.

Typically, manufacturers of anchor systems market suture anchors preloaded with suture(s) that the anchor has been designed and tested with; furthermore, the manufacturer’s Instructions for Use (IFU) will specify the type of suture and how many strands may be used with an anchor. Suture anchors are continuously evolving to improve anchor strength and to facilitate arthroscopic or open procedures. Soft suture anchors are the newer anchors on the market that have pursued fixation differently with the all-suture design. The Juggerknot 1.4 was the first all-suture construct that was designed to avoid potential sequelae from the migration and third body wear of a rigid anchor body, to provide radiographic images unobscured by metal hardware, and to facilitate revision procedures. The small 1.4 mm diameter of the drill hole helps to minimize compromise to the bone while allowing for multiple points of soft tissue fixation¹⁵.

Based on the injury type and the anatomical position of the injury, the single- and double-loaded Q-Fix™ Suture Anchor designs offer the surgeon more flexibility when determining the type of repair. The smaller footprint required by these devices allows the placement of multiple implants in a limited area, which promotes greater tissue-to-bone contact.

A summary of known and potential risks and benefits to humans can be found in the IFU.

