8.1.2 Device Information

The Q-Fix™ All-Suture Anchor System also known as the Q-Fix™ Soft Suture Anchor System/ Q-Fix™ Soft Suture Anchor/ Q-Fix™ Suture Anchor is available in 1.8 mm (single suture loaded) and 2.8 mm (double suture loaded) sizes; is manufactured from braided polyester with ultra-high molecular weight polyethylene (UHMWPE) suture; and is pre-loaded into a disposable tool designed to facilitate direct insertion into a pre-drilled or pre-punched bone hole. Table 8.1-1 demonstrates the model, specifications, dimensions and product description of the Q-Fix™ All- Suture Anchor System.

The Q-Fix™ MINI Suture Anchor minimizes bone removal by shortening the drill tunnel depth by 5mm. This drill depth of 17.1mm is approximately 23% shorter than the existing Q- Fix™ 1.8mm anchor.

[figure not shown]
[figure not shown]
[figure not shown]
CONFIDENTIAL AND PROPRIETARY

This document contains information that is confidential and proprietary to Smith & Nephew PLC and Smith & Nephew, Inc. and is intended for use only by Smith & Nephew and its manufacturer. It shall not be reproduced or copied in whole or in part, nor shall the contents be disclosed by any means without prior written permission from Smith & Nephew, nor shall anyone make any use of it that is contrary to the expressed or implied wishes of Smith & Nephew.

Study Protocol—Device	
Safety and Performance of Q-Fix™ All-Suture Anchor System	Number: 17-5010-11
	Version: 2.0 05SEP2019
	Page: Page 17 of 62

When the soft suture anchor is deployed into the predrilled/punched hole, the suture legs are tensioned, increasing the soft anchor’s diameter, locking the anchor suture against the cortical bone. The soft suture nature of the anchor allows the suture to be placed in a tunnel with a smaller diameter, preserving more bone.

Table 8.1-1: Product performance, structural composition and specification model of device

Model	72290123	25-1800	25-2800
Specification	1.8 mm MINI	1.8 mm	2.8 mm
Dimensions			
Diagram			
Product description	1.8 mm wide x 10mm long Q-Fix™ MINI All-suture Anchor, single-loaded with a #2 MAGNUMWIRE™ suture	1.8 mm wide x 15mm long Q-Fix™ All-suture Anchor, single-loaded with a #2 MAGNUMWIRE™ suture	2.8 mm wide x 20mm long Q-Fix™ All-suture Anchor, double-loaded with a #2 MAGNUMWIRE™ suture

CONFIDENTIAL AND PROPRIETARY

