#### 5. Study Endpoints

##### 5.1 Primary Endpoints

- Clinical success rate, defined as subjects without re-intervention at 6 months post- operative, as assessed by the surgeon

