##### 5.4 Exploratory Endpoints

- Clinical success rate as defined above, by anchor size

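### Success by anchor size is pooled over hip, shoulder and knee, so a difference between sizes cannot be separated from the joint treated

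*SAP*

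**What the plan says.** The exploratory endpoint in SAP 5.4 is "Clinical success rate as defined above, by anchor size". SAP 7.9.3 carries it out in one line: "Clinical success rate at 6 months and at 12 months for all subjects will be analyzed by anchor size". That line names no joint strata and no interval method.

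The endpoint it refers back to counts subjects: "Clinical success rate, defined as subjects without re-intervention at 6 months post- operative, as assessed by the surgeon" (SAP 5.1). The section headed "7.4.3 Derived Data for the Exploratory Endpoints" contains only N/A, so the SAP text has no rule that assigns a subject to a size.

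SAP 7.9.1 repeats the primary analysis separately for hip, shoulder and knee. SAP 7.9.2 applies the same type of analysis to 12-month success and to subjects aged 13 to 21. SAP 7.9.3 does neither.

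On what determines size, Protocol 5.1 says of suture anchors in general: "Patient bone density, repair location, potential allergies, the operation being performed and surgeon preference determine the size, type and composition of the anchor". The same section relates the choice between single- and double-loaded Q-Fix designs to the type and anatomical position of the injury. Protocol 8.1.2 ties loading to size: the system "is available in 1.8 mm (single suture loaded) and 2.8 mm (double suture loaded) sizes". Table 8.1-1 lists three models, two of them 1.8 mm wide (MINI and standard), and Amendment 1 (Protocol 23.3) speaks of three sizes. On the number of anchors, Protocol 5.1 says: "The smaller footprint required by these devices allows the placement of multiple implants in a limited area".

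**The concern.** Amendment 1 raised the maximum enrolment partly to admit more MINI subjects and allowed them a separate start date, so that data would exist on all three sizes. A reader of the final report will therefore look at the by-size table.

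If one size is used more often in a joint with more revisions, its pooled row looks worse even when the anchors perform identically. The pooled table gives no means of noticing this, although the same SAP already uses a by-joint layout for its other success tables.

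A second, conditional problem is the unit. Success belongs to the subject and size to the implant. A subject with anchors of two sizes would either fit no row or be counted in two, and one revision could then count against a size that held.

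**Working it through.** **Plan's own figure.** The only sample-size figure is by joint, not by size: 28 evaluable per joint at 5% loss is 28/0.95 = 29.5, rounded up to 30, and 3 × 30 = 90. This reproduces the stated minimum. No figure exists by anchor size, so there is none to check for this table.

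**Joint mix.** Amendment 1 reports 106 hip, 99 shoulder and 24 knee subjects: 229 in all, or 46.3%, 43.2% and 10.5%. The size mix within each joint is not given.

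**Artefact from pooling (assumed inputs).** Suppose size has no effect, so success depends only on the joint. The pooled rate for a size is then the sum over joints of (share of that size's subjects in the joint) × (success in the joint). Assume joint shares of 60/30/10% for size A, 40/40/20% for size B and 10/40/50% for size C.

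| Assumed joint success | Size A | Size B | Size C | False gap, A − C |
|---|---|---|---|---|
| 95/95/95% | 95.0% | 95.0% | 95.0% | 0 |
| 97/95/93% | 96.0% | 95.4% | 94.2% | 1.8 points |
| 98/95/90% | 96.3% | 95.2% | 92.8% | 3.5 points |

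Example, size C in the last row: 0.10 × 98 + 0.40 × 95 + 0.50 × 90 = 9.8 + 38.0 + 45.0 = 92.8%. In the extreme case where each size is used in one joint only, the last row gives 98 − 90 = 8 points. Within any one joint the gap is zero in every scenario, which is what rows by size within joint would show.

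**Mixed sizes (assumed share).** Take 90 subjects, of whom k have two sizes. Leaving them out gives rows that total 90 − k; counting them under each size gives 90 + k.

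| Assumed share | k | Left out | Counted twice |
|---|---|---|---|
| 5% | 4 | 86 | 94 |
| 10% | 9 | 81 | 99 |
| 20% | 18 | 72 | 108 |

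Mutually exclusive groups total 90 whatever the share. If there are no mixed-size subjects, k = 0 and the question disappears.

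**The case against.** The strongest reply is that this is one descriptive line in an uncontrolled case series. No test between sizes, hypothesis or decision rule is planned, and gaps of 2 to 3 points lie well inside the 11% precision that SAP 6.1 accepts. That is right and fixes the weight of the point: it is minor. It does not make the pooled table the better choice, because the by-joint layout is already in use.

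A reader might infer that size differences in the table *will* reflect the joint. The documents do not support that. The general sentence in Protocol 5.1 is background on suture anchors and lists repair location as one of five factors. No size-by-joint counts or joint-specific revision rates are given. What stands is that the two cannot be told apart.

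A reader might also infer that subjects did receive mixed sizes. Protocol 5.1 says only that the footprint "allows the placement of multiple implants in a limited area". Several anchors of one size cause no problem, and the protocol itself speaks of MINI subjects as a group. The table, figure and listing shells that accompany the SAP were not available and may define the rows. The mixed-size gap is therefore conditional.

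Nor do the documents show that this is the only output that separates the models. The adverse event tables in SAP 7.9.4 have device placeholders that may be by model, and SAP 7.6 plans a disposition table in terms of implants.

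**Conclusion.** The point holds as a limit on interpretation that an available layout would reduce. SAP 7.9.3 pools joints although the protocol links anchor choice to location, so a size difference in that table could come from size, joint or both.

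The magnitude cannot be computed from the documents. Under the assumptions shown, the artefact is 0 with equal joint rates, 1.8 to 3.5 points with partial overlap of size and joint, and up to 8 points if each size were confined to one joint.

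For MINI there is a further tangle. Protocol 9.1 allows a different enrolment start date for MINI subjects only, so MINI may also differ by period, and rows by joint do not remove that.

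**What to change.** In SAP 7.9.3, present 6- and 12-month success by anchor size within each joint as well as pooled, following the by-joint repeat in SAP 7.9.1.

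In SAP 7.4.3, replace N/A with mutually exclusive subject groups: MINI only, 1.8 mm only, 2.8 mm only, and mixed sizes if any occur. If none occur, the last group is empty and costs nothing.

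If the CRF identifies the model of the revised anchor, a descriptive row of anchors revised over anchors implanted, by model, may be added. That field could not be checked here, and such a row would ignore the clustering of anchors within subjects.

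Add a footnote that MINI subjects may come from a different enrolment period and that rows by joint do not adjust for it, nor for the procedure within a joint.

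The cost is a grouping variable, extra table rows and small cells. The 24 knee subjects at the amendment, spread over four groups, average 24/4 = 6 per cell. Even a cell of 10 with 10 successes has an exact 95% lower limit of 69.2%. That is tolerable in a descriptive exploratory table, provided that the counts are shown.
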